## **Girls Invest Study Procedures**

**A Two-armed Randomized-Controlled Trial** will be implemented across demographically similar communities and ensure adequate numbers recruited. Girls will be recruited from community and school-based partnerships. Groups of an average of 10-13 girls from each of 18 sites will be randomized to: 1) **Girls Invest** or 2) a wait-list control condition (n= 9 groups per arm; total of about 208 girls). Control condition participants will receive *Girls Invest* after 6 months follow-up.

**Inclusion Criteria.** Participants will include girls ages 15-22 years of age who are participating in local school-based and community programs primarily serving Latina adolescent girls in the San Diego area. Community partners include community-based health centers that have teen-focused programs. School based partnerships include high schools and community colleges. Randomization will be stratified by site type (i.e. we will randomly assign an equal number of high schools to be in the treatment group and control group; we will do the same for community colleges and community-based partnerships).

**Recruitment and Screening.** The project coordinator will be responsible for training and oversight of data collection staff. Data collection staff will consist of young females who will be trained on research ethics, all data collection activities, and sensitivity when working with this population.

Partnerships were developed between Girls Invest and community based programs as well as schools predominantly serving the Latinx community such as: City Heights, San Ysidro, Southeast San Diego, El Cajon, Vista, Chula Vista, and National City.

We will work with community based programs as well as local schools, and community colleges to conduct recruitment. These partnerships will involve our team going into particular programs or classes to recruit a group of adolescent girls. Given that some group-based programs and/or classes are still virtually held, we will hold orientation sessions either in-person or via zoom. These sessions will include a description of Girls Invest as well as the research study. Among girls who are interested, we will support them to download the app, complete consent forms via the app, and to take the baseline survey. Girls will also complete the savings account application. If parental consent is needed prior to the orientation, we may make arrangements for girls to download the app ahead of the orientation or provide the program with hard copies of the consent form for girls to have parents sign ahead of the orientation day (if in-person)

At schools, our recruitment may also include in-class presentations. Presentations will involve a presentation on financial literacy related topics, including how money and intimate relationships intersect, followed by a brief presentation of our Girls Invest program and study for those who may be interested. We will stay after class if anyone has questions or wants to enroll. The PI will not recruit in any of her own classes at SDSU. We will assure students that participation does not affect their grade in the class.

**Informed consent and data collection.** Informed consent for index participants will occur in-person during a group orientation or via a phone or online chat. The consent forms can be signed with hard copies or via the app. All index participants will be assigned a unique identifier to link baseline and follow-up assessments.

Parental consent will be obtained for those participants between the ages of 15-17 years. After signing the consent form, each eligible participant (<18 years of age) will be provided with two copies of the parental consent form, along with a stamped and addressed envelope, which can be used to mail back the signed parental consent form (one copy of the parental consent will be kept by the parent/guardian). Participants can also choose to do the signed parental consent via

the app. After signing their consent forms, all participants will be given access to the app (via a username and password); however, initially they will only have access to the resource sheet (providing local resources) along with consent forms, including forms for parental consent. Parents/guardians will be able to sign the consent via the app. All consent forms will be filed and stored separately from other app and survey data. Parental consent forms will be available in both English and Spanish.

Baseline and follow-up questionnaires will take approximately 45 minutes and will be self-administered via an online survey. During an initial orientation, as time permits, participants will take the online baseline survey during that time. The online surveys can be taken by participants on their own as well. If participants take the baseline survey on their own, participants will be encouraged to complete the questionnaire in a safe and private location. In cases where participants do not complete the app-based questionnaire on-time or need assistance, staff will provide assistance and offer to meet participants to complete the survey in-person. The survey requires an ID, which will be provided to participants. Upon completion, questionnaire data will not be accessible via the online platform nor the mobile device.

**Randomization and Retention.** Each group (n=18) will be randomized to study condition. Randomization will be stratified by site type (i.e. we will randomly assign an equal number of high schools to be in the treatment group and control group; we will do the same for community colleges and community-based partnerships). Participants randomized to the *Girls Invest* intervention will be notified with a brief orientation on how to use the app with contact information for study staff in case they have questions. App-based data on completion of modules and completion time will also be collected. Control group participants will be notified that they will be on the wait-list and complete the intervention after 6 months. Regardless of study condition, all participants will be linked to the online application for their savings accounts (ID can be uploaded online as well) upon completion of the baseline survey. For participants in the control group, accounts will become active after the 6 months follow up survey is complete. To maximize retention, incentive payments will be escalated: \$25 at baseline and \$30 at 6 months follow-up via Amazon e-cards. Participants will also be contacted via the app (or a phone call by study staff) every two months to update contact information. Those who do not complete follow-up questionnaires via the app will be contacted up to 4 times followed by contacting participant's alternate contacts, using methodology we have used effectively in previous studies. If these efforts are not successful, participants will be classified as non-respondents. Using similar tracking methods, our previous work with a similar sample achieved a 92% retention rate at 6 months follow-up.

**Assessing the feasibility, fidelity, acceptability, and scalability of *Girls Invest* (Aim 1).** Data logs will serve to monitor study progress in recruitment (e.g. proportion eligible, interested, refused, and ability to recruit at least 1 friend), participant retention (e.g., differential dropouts by condition), adherence (e.g., savings account enrollment), and adverse events. Information on recruitment and retention (as well as intra-cluster correlation of endpoints within social networks) will help inform sample size determination for a subsequent full-scale trial. Contamination will be assessed via items on the follow-up survey (e.g. control participants' knowledge of *Girls Invest* or any participants in the *Girls Invest* intervention). App-generated data will assess engagement with and completion of *Girls Invest* (e.g. # modules completed, time spent on each) and used to identify completers (80% of the *Girls Invest* modules) versus non-completers.

Evaluation of acceptability and receptivity will include in-depth interviews (up to n=30; similar proportions index participants and peers, 5 with non-completers) to evaluate participants' experiences with *Girls Invest* (e.g. content, app dynamics, savings account features), and identify mechanisms underlying any intervention effects (e.g. did the intervention affect

economic vulnerability? how did these effects influence girls' sexual and contraceptive decision-making? Were certain components most impactful?) These will take place via a phone or online call or in private space at La Maestra. Based on our previous work, we expect 20 interviews to be sufficient for saturation of themes; however, we will conduct additional interviews (up to an additional 10) if needed. Participants will be paid \$30 for in-depth interviews. For those participants who are <18 years of age, we will obtain parental consent using the main study consent form, rather than using a separate form for in-depth interviews. Details of the in-depth interviews will be provided in these main study parental consent forms. While details are included in the main study consent form for participants, we will also review all of the in-depth interview procedures and details in a separate consent form provided immediately prior to the in-depth interview.

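### No question that elicits adverse events is described, so harms would be logged passively: probably undercounted in both arms, and possibly unequally

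*Combined protocol and SAP*

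**What the plan says.** The Aim 1 section (feasibility, fidelity, acceptability and scalability) is the only place where adverse events appear. It opens "Data logs will serve to monitor study progress in recruitment" and ends the list of monitored items with "participant retention (e.g., differential dropouts by condition), adherence (e.g., savings account enrollment), and adverse events". No definition, eliciting question, schedule or by-arm report follows. The same section does say how contamination will be measured, namely by follow-up survey items; nothing comparable is said for adverse events.

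The Randomization and Retention section describes the contacts:
- **Both arms:** "Participants will also be contacted via the app (or a phone call by study staff) every two months to update contact information".
- **Girls Invest arm:** participants "will be notified with a brief orientation on how to use the app with contact information for study staff in case they have questions".
- **Control arm:** "Control group participants will be notified that they will be on the wait-list and complete the intervention after 6 months". Controls' savings accounts become active only once the 6-month survey is done.

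Both arms also complete the surveys: "Baseline and follow-up questionnaires will take approximately 45 minutes and will be self-administered via an online survey" (Informed consent and data collection). The survey items are not reproduced in the documents.

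**The concern.** A log with no eliciting question behind it records what participants choose to mention. The participants are aged 15 to 22, and the programme's subject matter includes how money and intimate relationships interact. Plausible harms, such as conflict over money or loss of privacy, are ones a girl may well not raise unprompted. The protocol recognises this sensitivity when it encourages privacy for baseline surveys taken alone.

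Two things are at stake. First, a short list of logged events could be taken as reassurance when nobody was described as asking. Second, the occasions for mentioning an event are not described as identical in the two arms, so an imbalance in the log could reflect contact rather than harm. Once controls receive Girls Invest after 6 months, a concurrent untreated comparison cannot be rebuilt.

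**Working it through.** The documents state no adverse-event rate or reporting rate, so there is no planned figure to reproduce. The check sets the described routes side by side and then illustrates the consequence.

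**Routes by which an event could reach staff before 6 months**

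| Route | Girls Invest | Control |
|---|---|---|
| Two-month contact | Yes; stated purpose is contact details | Same |
| Follow-up survey | Yes; no adverse-event item described | Same |
| Post-randomization orientation with staff contact details | Described | Not described; wait-list notice only |
| Modules in use | Yes | After 6 months |
| Live savings account | Implied by the control-arm restriction | After the 6-month survey |
| In-depth interview | Possible; timing not stated | Topic is experience of Girls Invest, so not before crossover |

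The two shared routes have no described safety question. The remaining rows are where capture could differ.

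**Illustration.** Inputs: about 208 girls in two arms (opening paragraph of the procedures), so 208 / 2 = 104 per arm. True risk and capture probabilities are assumptions.

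Expected logged events = n × true risk × capture probability.

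- Full capture, 10% risk: 104 × 0.10 × 1 = 10.4 in each arm; ratio 1.0.
- Equal but partial capture of 40%: 104 × 0.10 × 0.40 = 4.2 in each arm; ratio still 1.0, but 60% of events are missed.
- Capture 50% v 40%: 5.2 v 4.2; ratio 0.50 / 0.40 = 1.25.
- Capture 60% v 40%: 6.2 v 4.2; ratio 1.5.
- Capture 60% v 30%: 6.2 v 3.1; ratio 2.0.
- Capture 60% v 30% at other risks: 3.1 v 1.6 (5%) and 12.5 v 6.2 (20%); ratio 2.0 in each case.

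With equal true risk, the logged ratio is simply the ratio of the two capture probabilities. The undercount needs no difference between arms; the distortion of the comparison does.

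**Interviews.** If 20 to 30 interviews took place in the Girls Invest arm before 6 months (an assumption), 20 / 104 = 19% to 30 / 104 = 29% of that arm would have a one-to-one conversation that controls lack. If they took place later, they would not affect the 6-month comparison.

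**The case against.** The strongest reply is that most of the arm difference is inferred. All girls meet staff at recruitment and consent, staff offer survey help to anyone, and both arms get the two-month contact and non-response follow-up. The consent pages are not available to this review and may give staff contact details to everyone. Neither the arm nor the timing of the interviews is stated, and nothing says that interview reports feed the log. The illustration cannot settle the matter, since its ratio is whatever capture rates are assumed. All of this stands, and it reduces unequal capture to a possibility.

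Four stronger readings are tempting, and the documents do not support them:
- **That participants are never asked about harm.** The survey items and the content of Figure 1 are not shown, so an outcome item bearing on harm cannot be excluded. Only the absence of a described question is established.
- **That the log will favour one arm by a known amount.** No reporting rate is given for either arm.
- **That a planned comparison of harms is invalid.** The Aim 2 section plans outcome models and tests of baseline imbalance and attrition, but no between-arm analysis of adverse events.
- **That the adverse-event log is intended to shape the later full-scale trial.** The Aim 1 section links only recruitment, retention and intra-cluster correlation to that trial's sample size.

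What survives is that no eliciting question is described, and that the one recurring shared contact has a stated purpose unrelated to safety.

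**Conclusion.** The point holds as a gap in how harms are ascertained. Following the text, staff could make every scheduled contact in both arms without asking about harm. Undercounting in both arms is probable; unequal capture is possible, most plausibly towards more logged events under Girls Invest. Neither can be sized from the documents, and the figures above are illustration only. Few logged events should not be read as evidence of safety, nor an imbalance as evidence of harm in one arm.

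The conclusion assumes that the undisclosed survey items contain no harm question asked alike in both arms. If they do, the sponsor need only say so and report those items by arm. The matter does not threaten the Aim 2 analyses; it is an inexpensive improvement worth making before follow-up starts.

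**What to change.** 1. Put the same short, arm-neutral adverse-event items in the 6-month survey for both arms: for example, whether anything bad or upsetting has happened involving money, a partner, family or privacy, and, separately, whether it seemed linked to the study. State what counts as an adverse event.
2. Where privacy allows, add the same items to the two-month contacts in both arms.
3. Tabulate solicited events by arm, with the number of girls asked and answering as denominators. At the plan's assumed 20% attrition, about 104 × 0.80 = 83 per arm would answer at 6 months, so the denominator matters.
4. List volunteered and interview-derived reports separately, with their source, outside the arm comparison.
5. Add a question on unwanted effects to the interview guide, including for the 5 non-completers.

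No extra visits or participants are needed. The costs are a few more items, more events for staff to review, and disclosures, some from minors, that must go through the study's own handling procedure; the documents available here do not describe one, so the sponsor should confirm it covers these items. Privacy is the main constraint on the two-month contacts, which is why the 6-month survey should carry the core items.

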**Statistical Power and Analyses on Economic, Social, and Health Behavior Risks. (Aim 2)**

Sample size calculation is based on intermediate outcomes (Figure 1) with at least 25% prevalence at baseline. To achieve 80% power, we will require 208 participants (approximately 13 in each of 16 groups) to be able to determine a moderate effect size of 0.52 (26% difference between the two arms on intermediate factors in Figure 1), using an intra-class correlation coefficient (ICC) of 0.03 given the group structure, type I error of 0.025, and 20% attrition (conservatively estimating 80% retention over 6 months). Note the sample size has taken multiple comparisons (using Bonferroni adjustment) into account. In addition, we may likely have a lower ICC, which would afford greater statistical power.

To assess clustering within groups (n=18), random effects models will calculate ICCs. We will conduct intent-to-treat analyses using crude and adjusted mixed effects logistic and linear regression models with a focus on intermediate variables (Figure 1) to assess group-by-time effects, with adjustments for clustering and intervention engagement and completion. To assess random imbalances (at baseline) and differences in attrition by condition, we will perform chi-square analyses and t-tests. We will adjust for relevant covariates to address imbalances between conditions. Differences in attrition between study conditions will be noted as potential threats to validity. We will also explore variations in observed intervention effects by savings behaviors, module completion, as well as relevant factors identified via in-depth interview findings.

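### The 80% power is worked for 16 groups, but 18 are randomized, and with no small-sample method named the Bonferroni-adjusted 0.025 is not secured

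*Combined protocol and SAP*

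**What the plan says.** The Aim 2 power paragraph gives the size as "To achieve 80% power, we will require 208 participants (approximately 13 in each of 16 groups". The target is a "moderate effect size of 0.52 (26% difference between the two arms on intermediate factors in Figure 1", for outcomes with a baseline prevalence of at least 25%. The other inputs are an ICC of 0.03, a type I error of 0.025 and 20% attrition. On multiplicity it adds: "Note the sample size has taken multiple comparisons (using Bonferroni adjustment) into account". It gives neither the formula nor the sidedness of 0.025.

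Elsewhere the number of groups is 18. The design paragraph of Girls Invest Study Procedures has 18 sites, 9 groups per arm, an average of 10-13 girls per group and about 208 girls in all. Under Randomization and Retention: "Each group (n=18) will be randomized to study condition". The analysis paragraph that follows the power paragraph says: "To assess clustering within groups (n=18), random effects models will calculate ICCs".

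The analysis will use "crude and adjusted mixed effects logistic and linear regression models with a focus on intermediate variables (Figure 1) to assess group-by-time effects". No degrees-of-freedom rule or other small-sample correction is given.

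**The concern.** Two things do not fit together. First, the power figure describes 16 groups of 13, while the trial randomizes and analyses 18 groups averaging 208/18 = 11.6. Second, whole groups are randomized, so the arm effect is judged against variation among 18 groups. With so few groups, a normal reference tends to reject too often. The plan has spent power on a Bonferroni adjustment to 0.025, yet says nothing about how that level is kept in the mixed models. A reader of an Aim 2 result cannot tell whether 80% power and a 0.025 error rate were both in force. The same section of the plan's aims says the study will inform the sizing of a later full-scale trial, so an unclear basis could be carried forward.

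**Working it through.** **Inputs.** From the power paragraph: 208 girls, 16 groups, ICC 0.03, type I error 0.025, 80% retention, 26-point difference, 25% prevalence. From the design and randomization sections: 18 groups. Assumed: 0.025 is two-sided; the control rate at follow-up equals the 25% baseline figure, so the comparison is 25% vs 51%; outcomes are compared at follow-up only.

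**1. The plan's own figure (16 groups).**
- Retained per group: 13 × 0.8 = 10.4.
- Design effect: 1 + (10.4 − 1) × 0.03 = 1.282.
- Needed per arm before clustering: [2.2414 × √(2 × 0.38 × 0.62) + 0.8416 × √(0.25 × 0.75 + 0.51 × 0.49)]² / 0.26² = 64.9, rounded up to 65.
- Total: 2 × 65 × 1.282 / 0.8 = 208.3, against 208 printed.
- In reverse: 166.4 / 1.282 / 2 = 64.9 effective girls per arm, power 79.97%.

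The same inputs with a t reference on 14 df give 70.3-73.8%, so under this reading the printed 80% implies normal quantiles.

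**2. 18 groups, still with normal quantiles.** Retained per group 208 × 0.8 / 18 = 9.24; design effect 1 + 8.24 × 0.03 = 1.247; effective girls per arm 83.2 / 1.247 = 66.7; power 81.2%.

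**3. 18 groups, t reference on 18 − 2 = 16 df.** The critical value rises from 2.241 to 2.473. With the pooled variance the noncentrality is 0.26 / √(0.4712/66.7) = 3.09 and power is 72.8%. With the unpooled variance it is 0.26 / √(0.4374/66.7) = 3.21 and power is 76.2%.

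**4. Simulation** (beta-binomial data, ICC 0.03, 18 groups, 166 girls, follow-up only, 100,000 runs per scenario).

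| Test | Type I error | Power, 25% vs 51% |
|---|---|---|
| Mixed logistic, normal reference | 0.029-0.030 | 81.6% |
| Mixed logistic, t on 16 df | 0.016-0.018 | 74.9% |
| Mixed logistic, critical value calibrated (2.31-2.33) | 0.025 | 79-80% |
| Cluster-level t-test, 16 df | 0.025 | 75.0% |
| Cluster-level test, normal critical value | 0.039 | not used |

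A check on a continuous outcome at 0.536 SD in a linear mixed model shows the same pattern: normal reference, error 0.029 and power 77.6%; t on 16 df, 0.016 and 70.3%; calibrated, about 76%.

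**5. Sensitivities, formula on 16 df, 25% vs 51%.**

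| Change | Power |
|---|---|
| 92% retention | 77.7-80.9% |
| ICC 0.01 (assumed) | 79.2-82.3% |
| 92% retention and ICC 0.02 (assumed) | 81.0-84.1% |
| 18 groups of 13 (234 girls) | 76.9-80.2% |
| 18 groups of 10 (180 girls) | 67.3-70.9% |
| 0.025 read as one-sided | 82.7-85.4% |

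The documents give no correlation r between baseline and follow-up. For continuous outcomes, baseline adjustment multiplies the variance by 1 − r², and an r of about 0.29-0.38 would bring power on 16 df back to 80%. A change score multiplies it by 2(1 − r) and would need about 0.54-0.57. The group-by-time model itself was not simulated.

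**6. The printed 0.52.** It equals 0.26/0.5. The pooled standardized difference for 25% vs 51% is 0.26/√(0.38 × 0.62) = 0.536.

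**The case against.** The strongest reply is that the plan's 80% is sound. It can be reproduced, 18 groups improve it slightly, and a mixed logistic test calibrated to exactly 0.025 keeps 79-80%. The inflation under a normal reference is small. The inputs are also cautious: the plan cites earlier work, "our previous work with a similar sample achieved a 92% retention rate at 6 months follow-up", and says "In addition, we may likely have a lower ICC, which would afford greater statistical power". Baseline data in the group-by-time model could add power.

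Most of this stands, and it limits the point. A reader might infer three stronger things that the documents do not support:

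- **That the trial's real power is 73-76%.** That range is a formula result for a follow-up-only comparison on 16 df. In the mixed logistic model a t reference on 16 df over-corrects, and the group-by-time analysis may do better or worse, depending on a correlation the plan does not give.
- **That 208 or 80% is a calculation error, or that 18 groups cost power.** Neither is so.
- **That 0.52 is a wrong input.** The 26-point difference is printed beside it, so this is a matter of clarity only.

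Sidedness is also not settled by the arithmetic. One-sided 0.025 gives 87.1% for the plan's inputs without a continuity correction, which favours the two-sided reading. But one-sided 0.025 with a continuity correction and a design effect of 1 + 12 × 0.03 = 1.36 gives 207.4, also close to 208.

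What the reply does not remove is the wrong group count behind the stated power, and the absence of any method for holding 0.025 with 18 groups.

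**Conclusion.** The point holds in a limited form, with minor to moderate severity. The power paragraph describes 16 groups where the trial has 18; this needs no assumption to see. The lack of a small-sample method leaves the type I error of the mixed models modestly above the intended level, about 0.029-0.030 against 0.025. Restoring 0.025 brings power for 25% vs 51% to somewhere between about 80% and 73%, depending on the method chosen. These sizes rest on a two-sided 0.025, a 25% control rate at follow-up, an ICC of 0.03, 80% retention and no use of baseline data.

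**What to change.** With enrolment and randomization unchanged, revise the Aim 2 power and analysis paragraphs:

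- (a) Use 18 groups, with a mean of 11.6 enrolled and 9.2 retained per group.
- (b) Say that 0.025 is two-sided, if it is, and give the two assumed proportions beside the 26-point difference.
- (c) Name a small-sample inference method for the mixed models that holds the error at 0.025, such as a degrees-of-freedom correction, a parametric bootstrap or a permutation test that respects the stratified group allocation.
- (d) Restate power for that method, within roughly 73-80% at an ICC of 0.03 and 80% retention. Label it follow-up-only, and show higher retention, a lower ICC and an assumed baseline correlation as sensitivities.

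The cost is rewording and a short calculation. The stated power becomes slightly less favourable. A plain t reference on 16 df would be simple but conservative in the mixed logistic model, so a better-calibrated method is worth the extra effort.

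### The planned group-by-time test leaves the baseline arm difference free, which is valid but less precise than a 6-month comparison adjusted for each girl's baseline value

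*Combined protocol and SAP*

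**What the plan says.** The Aim 2 section (Statistical Power and Analyses) plans "mixed effects logistic and linear regression models with a focus on intermediate variables (Figure 1) to assess group-by-time effects, with adjustments for clustering". The model terms are not written out. The only covariate rule is "We will adjust for relevant covariates to address imbalances between conditions". It is tied to imbalance, which is to be examined with chi-square and t-tests, and it names no variable.

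Under Informed consent and data collection: "All index participants will be assigned a unique identifier to link baseline and follow-up assessments". Follow-up is at 6 months, so each girl has at most two linked measurements.

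The power statement in the Aim 2 section concerns a "26% difference between the two arms on intermediate factors in Figure 1", with "type I error of 0.025, and 20% attrition", an ICC of 0.03 and 208 girls. It gives no correlation between baseline and follow-up.

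Under Randomization and Retention: "Each group (n=18) will be randomized to study condition". At orientation sessions, for girls who are interested, "we will support them to download the app, complete consent forms via the app, and to take the baseline survey". No section says whether a site's allocation is made or known before its girls enrol and complete that survey.

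**The concern.** With two time points and terms for arm, time and arm-by-time, the interaction estimates the arm difference in change and leaves the baseline arm difference free. If girls enrol before allocation, the expected baseline difference is zero. Estimating it anyway spends information. Adjusting for the girl's baseline value, or constraining the baseline means to be equal, recovers it.

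Two things are at stake. One is precision, which is scarce with 18 randomized groups and can be gained here from data already being collected. The other is the meaning of the 80% power. The power of a change contrast depends on the baseline-to-follow-up correlation, and the sample size statement contains none.

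**Working it through.** **1. The plan's own figure.** Inputs from the Aim 2 section: prevalence 25% against 25 + 26 = 51%, type I error 0.025, power 80%, ICC 0.03, 13 girls per group, 20% attrition. Whether 0.025 is one- or two-sided is not stated. Three one-timepoint two-proportion routes come close to 208:

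- Unpooled variance, two-sided 0.025: (2.241 + 0.842)² × (0.25×0.75 + 0.51×0.49) / 0.26² = 61.5 per arm. The design effect is 1 + 12×0.03 = 1.36. Total: 2 × 61.5 × 1.36 / 0.8 = 209.
- Pooled variance, two-sided 0.025: 65 per arm. The design effect on the retained group size of 10.4 is 1 + 9.4×0.03 = 1.282. Total: 2 × 65 × 1.282 / 0.8 = 208.3.
- Continuity-corrected, 0.025 taken as one-sided: 61 per arm. Total: 2 × 61 × 1.36 / 0.8 = 207.4, or 208 rounded up.

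The documents do not say which was used. None of the three contains a baseline-to-follow-up correlation.

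**2. Setup for the comparison (continuous outcome).** From the documents: 9 groups per arm; 208/18 = 11.6, taken as 12 girls per group at baseline; 11.6 × 0.8 = 9.2, taken as 9 at follow-up; ICC 0.03; effect 0.52 SD. Assumed: within-girl correlation π = 0.3/0.5/0.7, group autocorrelation a = 0.8 (also 0.5 and 1.0), two-sided alpha 0.025, 18 − 2 = 16 degrees of freedom, dropout unrelated to outcome.

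With total variance 1, the covariances are:
- same girl, two times: 0.97π + 0.03a
- two girls in a group, same time: 0.03
- two girls in a group, different times: 0.03a

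**3. Both models keep girls without follow-up.** Generalized least squares with known variances; power from the noncentral t with noncentrality 0.52/SE. The constrained model drops the arm main effect.

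| π (a = 0.8) | 0.3 | 0.5 | 0.7 |
|---|---|---|---|
| Free group-by-time, SE | 0.182 | 0.158 | 0.128 |
| Baseline means equal, SE | 0.159 | 0.144 | 0.121 |
| Variance ratio (unrounded SEs) | 1.31 | 1.21 | 1.13 |
| Power, free | 65% | 78% | 93% |
| Power, constrained | 78% | 86% | 96% |

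The gain is about 13/8/2–3 points. At a = 0.5 it is 15/11/5 points, and at a = 1.0 it is 11/6/1.

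**4. Simple 6-month model, girls with follow-up only.** With 9 girls per group and slope b = π, the per-girl variance is V − 2bC + b²V, where V = 0.97 + 9×0.03 = 1.24 and C = 0.97π + 9×0.03×0.8 = 0.507/0.701/0.895. This gives 1.047/0.849/0.595. SE = √(2 × variance/81) = 0.161/0.145/0.121, and power is 77/86/96%. Omitting girls without follow-up therefore costs at most about 0.002 in SE in this setting.

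**5. Completers-only formula.** If the free model also used only girls with follow-up, the variance ratio would be 2/(1 + r), with r the baseline-to-6-month correlation of group means: r = 0.411/0.567/0.722 and ratio 1.42/1.28/1.16. A mixed model keeps all girls, so the smaller ratios in step 3 are the relevant ones.

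**6. Yes/no outcomes.** A simulation on the prevalence scale used 25% against 51%, 18 groups of 9, a = 0.8 and within-girl phi of about 0.30/0.47/0.62. It compared group means by t-test and gave 70/80/89% for change against 81/87/92% for the baseline-adjusted value. This points the same way, but it is not the planned mixed logistic model, for which adjustment also alters the odds ratio being estimated.

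**7. If allocation influenced who enrolled.** A stable baseline difference of 0.1 SD shifts the adjusted estimate by (1 − b) × 0.1 = 0.07/0.05/0.03 SD at slope 0.3/0.5/0.7. Mean squared error, adjusted against free:

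- At 0.1 SD: 0.07² + 0.161² = 0.031 against 0.182² = 0.033 (π = 0.3); 0.024 against 0.025 (0.5); 0.0155 against 0.0164 (0.7).
- At 0.2 SD: 0.046 against 0.033; 0.031 against 0.025; 0.018 against 0.016.

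The adjusted test's type I error would be about 3.7/3.2/2.9% at 0.1 SD and 7.6/5.6/4.1% at 0.2 SD, against a nominal 2.5%.

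**The case against.** The planned test is valid and in common use. The study is partly preparatory, since its recruitment, retention and clustering data "will help inform sample size determination for a subsequent full-scale trial". The model terms are unwritten: a two-time model with a common baseline mean could also be described as assessing group-by-time effects, and the unnamed covariates could include the baseline outcome. The gain is only 1 to 5 points at a within-girl correlation of 0.7, and the outcomes are in a figure that is not shown, so where this trial falls in the range is unknown. If allocation preceded enrolment, only the free model absorbs a stable baseline difference.

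Most of this stands as a limit on the point. It does not remove the point, because the text as written commits to neither adjustment nor constraint and ties covariates to imbalance. The timing objection stands in full and makes the recommendation conditional.

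A reader might infer that the trial is underpowered, for instance by setting the 65% above against the protocol's 80%. The documents do not support that. The 65% uses 16 degrees of freedom and an assumed correlation. With the same small-sample reference and completers only, a one-timepoint comparison has about 70% power, against 62/77/93% for the change contrast. The group-by-time test is therefore weaker at low correlation and stronger at high correlation. Nor do the documents state that 208 came from a one-timepoint calculation. That is an inference from the fit of several formulas.

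**Conclusion.** On the standard reading of the model, the plan forgoes precision that its linked surveys already offer. For continuous outcomes the free model's variance is about 1.13 to 1.31 times that of the constrained model at group autocorrelation 0.8. The power gain from adjustment is about 1 to 15 points as autocorrelation runs from 1.0 to 0.5 and within-girl correlation from 0.7 to 0.3. All of these correlations are assumed. The gain over the planned mixed logistic model is not established. The 80% cannot be attributed to the group-by-time test, but that test is not shown to fall short of it. The matter is worth correcting before analysis. It is not an error that invalidates the plan.

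**What to change.** State whether each girl's baseline survey is completed before her site's allocation is known.

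- **If it is:** make the primary estimate the 6-month arm difference adjusted for the girl's baseline value of the outcome, with a group random effect. For continuous outcomes, a two-time model with baseline means constrained equal is an alternative that keeps girls without follow-up. Keep the free group-by-time model as a sensitivity analysis.
- **If allocation could be known before enrolment or baseline:** keep the free group-by-time model as primary and report the adjusted estimate beside it.

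Write out the model terms in either case. State that the 80% refers to a two-arm comparison without a baseline-to-follow-up correlation, or restate it over a range of correlations.

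The cost is wording; no new data are needed. The simple adjusted model omits girls without follow-up (20% planned), the constrained model may be hard to fit with 18 groups, and either would be biased by a baseline difference that arose from allocation-influenced enrolment.
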